Among survivors found to be underdiagnosed or undertreated (Aim 1), in a randomized controlled design, compare changes in blood pressure, lipid, and blood glucose values from baseline to 1-year between those receiving the intervention (providing clinical results and survivorship care plans [SCPs] to participants and their healthcare providers, supplemented by clinician-led remote counseling sessions with participants to review SCP contents and teach CV risk factor self-management strategies) vs. control (providing clinical results without SCP to participants and their healthcare providers; with delayed access to the intervention).

- *Hypothesis: At the 1-year follow-up home visit, survivors randomized to the intervention arm will have a lower probability of having an undertreated CV risk factor compared with survivors in the control arm.*

3.1.3 Primary Aim 3

Determine barriers among (Aim 2) survivors (at baseline and 1-year: knowledge of

past cancer treatment, self-efficacy, health-related attitudes, medication adherence) and their primary healthcare providers (at 1-year only: knowledge and self-efficacy towards childhood cancer survivorship care) that contribute to undertreatment of hypertension, dyslipidemia, and diabetes.

- *Hypothesis 1: At baseline, underdiagnosis and undertreatment will be associated with lower knowledge, self-efficacy, and medication adherence, as well as a “self-controlling” health attitude among survivors.*
- *Hypothesis 2: At 1-year follow-up, intervention-arm participants will report improved knowledge, self-efficacy, and medication adherence vs. controls; healthcare providers who received the SCP will report improved knowledge and self-efficacy towards CV risk and survivorship care vs. providers of controls.*

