8.1 Baseline Questionnaire

This will include items on: 1) past medical history, 2) current health and medication adherence, 3) lifestyle habits, and 4) attitudes towards healthcare and current mood (**Table 4; Appendix**).

TABLE 4. Components of baseline questionnaire, exclusive of questions on past medical history and lifestyle habits.

*Health-related self-efficacy⁵⁶	10-item (4-point Likert scale) survey (will be reduced to 5-items) that measures perceived ability to set-goals, cope and recover from setbacks. Results have been found to be a strong predictor of subsequent health behavior change. ⁹⁶
*PROMIS anxiety & depression^{57,58}	These domains (adult 4-item survey; all 5-point Likert scale) are of secondary interest. Prior research via a longer instrument (Profile of Mood States) did not show SCPs associated with mood changes or anxiety. ^{50,85}
*Multidimensional Health Locus of Control [MHLC]⁵⁹	18-item survey (6-point Likert scale) will classify participants with regards to their attitudes towards healthcare screening into “worried”, “collaborative” and “self-controlling” typologies, which have been associated with differential likelihoods of obtaining recommended screening in retrospective CCSS analyses. ⁷⁸
*Medication Adherence Scale (MMAS-4)⁶⁰	Well-established 4-item (0=high, 1-2=medium, 3-4=low adherence) instrument initially used to study hypertension, but since validated for other diseases. ¹⁰⁰ Will be administered separately for blood pressure, lipid, and diabetes medications. Secondary analyses will examine adherence by medication burden.

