8.8 Primary healthcare provider measurements

Following the 2nd home visit, accompanying the mailing of a copy of participant materials (intervention group: clinical results and SCP; control group: clinical results only), all designated providers will be asked to answer questions adapted from the NCI/ACS SPARCCS (see **Appendix**).⁶¹

We will also request outpatient clinical records (clinician notes, medication lists, laboratory results) spanning the study period (and up to 2 years prior to the 1st home visit) from all participants' primary healthcare providers. We will abstract records for: 1) documentation of the participant's prior cancer history and CV risk status in relation to past cancer exposures; 2) any reference to a SCP or long-term follow-up guideline; 3) any CV screening planned or undertaken [coded separately]; 4) presence of any of the three target CV risk factors as a diagnosis/problem; and 5) interventions to address any CV risk factor [coding lifestyle or drug prescription separately]. Medications will be reviewed to examine whether, among those undertreated at the 1st home visit, there is subsequent treatment intensification (e.g., going from lifestyle prescription alone to adding medication; from lower to higher drug doses; from single to multiple drugs; **Table 7**), and whether treatment intensity differs across study arms after the intervention.

Medication (class)	Low	Medium	High
Hypertension			
Lisinopril (ACE-inhibitor)	≤10	11-30	>30
Amlodipine (calcium channel blocker)	≤2.5	2.6-9.9	≥10
High cholesterol			
Simvastatin (HMG CoA reductase inhibitor)	<20	20-39	≥40
Diabetes			
Glipizide (sulfonylurea)	<10	10-19	≥20
Insulin			Any dose

Description of how the study will engage with primary healthcare providers is otherwise described in **Section 7.5**.

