13.3 Aim 3 Analytic Plan

Hypotheses: 1) at baseline, underdiagnosis & undertreatment are associated with lower knowledge, self-efficacy, and medication adherence (if applicable), as well as a “self-controlling” health attitude among survivors; 2) at 1-year follow-up, compared with the control arm, the intervention arm will be associated with improved knowledge, self-efficacy, and adherence rates among survivors, and improved knowledge and self-efficacy among healthcare providers.

Baseline survivor-specific factors: Using data from all Aim 1 participants, determine whether those underdiagnosed and undertreated at the time of the 1st home visit have lower knowledge (i.e., less accurate recall of prior anthracycline or chest radiotherapy exposures [chi-square test]) and lower health-related self-efficacy [t-test or Wilcoxon rank-sum] compared with those not affected. Similarly, among those who report medications for the CV risk factors of interest, determine whether those undertreated have lower medication adherence (i.e., lower mean MMAS-4 scores [t-test or Wilcoxon

rank-sum]) vs. those not undertreated. Finally, determine if different health-related behavioral attitudes (“worried”, “collaborative” and “self-controlling”)⁶⁹ are associated with differential rates of underdiagnosis and undertreatment [chi-square test]. *A priori*, we hypothesize that the proportion undertreated will be greatest among “self-controlling” survivors vs. “collaborative” and “worried” (least undertreated) survivors. In subanalyses, we will analyze underdiagnosed participants (i.e., newly diagnosed per 1st home visit) separately from those undertreated (i.e., existing diagnosis but not meeting standard therapeutic goals) relative to the referent group (those without any abnormal CV risk factor). We also will use a combined logistic regression model to determine if knowledge, medication adherence, and health-related behavioral attitudes remain associated with underdiagnosis and undertreatment (combined and separately) after multivariate adjustment. Exploratory covariates are similar as before, and include sex, current age, insurance status, healthcare utilization, self-perceived CV risk, and family history of CV disease.

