Post-intervention analysis: Among Aim 2 participants (and their designated healthcare provider), we will examine the differences between intervention and control groups following the 2nd home visit with respect to 1) survivor knowledge [chi-square test], 2) survivor self-efficacy [t-test or Wilcoxon rank-sum], 3) survivor-reported medication adherence [t-test or Wilcoxon rank-sum], and 4) provider-reported knowledge and self-efficacy [chi-square tests] related to the care of childhood cancer survivors. All analyses will be intent-to-treat and include all survivors and providers with available end points. Subanalyses can stratify these outcomes by initial underdiagnosis vs. undertreatment status. *We also will analyze practice changes over the 1-year intervention period using clinical records.* This includes comparing [chi-square test] whether documentation rates differ across study arms of: 1) any CV-related screening, 2) CV-related interventions [both lifestyle and drug prescriptions], and 3) treatment intensity (**Table 7** earlier). If any survivors share the same healthcare provider, we will apply bootstrap methods to account for the effects of clustering. In secondary analyses, we will determine, via logistic regression adjusting for randomization status, whether providers of survivors who remain undertreated have lower self-reported knowledge and self-efficacy related to the care of childhood cancer survivors vs. providers of survivors no longer undertreated.

Sample size: For covariates assessed at baseline in Aim 3, we will be able to detect differences $\geq 5\%$, RRs $\leq 0.8 / \geq 1.2$, and $\geq 20\%$ of 1 standard deviation (**Table 10**). Among randomized participants (240/arm) and subanalyses (e.g., analyzing undertreatment, underdiagnosis separately: $\sim 75-150$ /arm), detectable differences will be less.

Covariate frequency	Baseline* N=320:480	Post-intervention & subanalyses		
		240:240	150:150	75:75
10% (e.g., primary care provider self-efficacy towards childhood cancer survivorship care ^{27,28})	5%/17% RR 0.5/1.7	3%/20% RR 0.3/2.0	2%/22% RR 0.2/2.2	- /28% RR -/2.8
25% (e.g., MHLC self-controlling or worried typologies ⁶⁹ ; survivor anthracycline self-knowledge ⁷⁰)	17%/34% RR 0.7/1.4	15%/37% RR 0.6/1.5	12%/40% RR 0.5/1.6	8%/47% RR 0.3/1.9

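### The 1-year medication-adherence comparison will in practice be made among survivors with a drug to score at follow-up, a set formed after randomisation, so it is not intent-to-treat, and Table 10 sizes it as if everyone had a score

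*Combined protocol and SAP*

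**What the plan says.** Medication adherence is among the secondary endpoints in the synopsis. It is also part of Aim 3 Hypothesis 2 (section 3.1.3), which predicts that "intervention-arm participants will report improved knowledge, self-efficacy, and medication adherence vs. controls".

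The instrument is the MMAS-4 (section 8.1, Table 4), scored "0=high, 1-2=medium, 3-4=low adherence". Table 4 adds: "Will be administered separately for blood pressure, lipid, and diabetes medications".

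For the baseline analysis, section 13.3 recognises that the scale does not apply to everyone. The hypothesis is worded as "lower knowledge, self-efficacy, and medication adherence (if applicable"), and the comparison is made "among those who report medications for the CV risk factors of interest".

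For the 1-year analysis, section 13.3 lists "survivor-reported medication adherence [t-test or Wilcoxon rank-sum"] as a between-arm comparison with no such restriction. It then states: "All analyses will be intent-to-treat and include all survivors and providers with available end points". It gives no rule for survivors on no relevant drug, for those who start one during the year, or for those who stop.

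Drug treatment is itself an outcome. Section 8.8 looks for treatment intensification, with the examples "going from lifestyle prescription alone to adding medication; from lower to higher drug doses; from single to multiple drugs", and asks whether treatment intensity differs by arm. Section 13.3 tests drug prescriptions and treatment intensity between arms.

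**The concern.** An intent-to-treat comparison needs an outcome that is defined for every randomised survivor, or for a subset fixed before randomisation. A survivor on no relevant drug does not have a missing MMAS-4 score; the score does not exist. Whether it exists at 1 year depends on events during the year, and those are events the intervention is designed to influence.

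If more intervention survivors start a drug, that arm's scored group will contain more recent starters. Should starters differ in adherence from established users, the arm means would differ even though no individual's adherence had changed. Success in getting survivors treated could then look like worse adherence, or like better adherence if starters are unusually diligent. If survivors who stop a drug give no score, unequal stopping has a similar effect.

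The same gap affects the stated power. The MMAS-4 row of Table 10 uses the full randomised count.

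**Working it through.** **1. Reproducing Table 10.** The inputs are 80% power and two-sided α = 0.05, which are stated for Aims 1 and 2 and assumed to carry over. The detectable difference in SD units is (1.960 + 0.842) × √(1/n₁ + 1/n₂).

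| Column | Computed | Table 10 |
|---|---|---|
| 320:480 | 0.202 | 20% |
| 240:240 | 0.256 | 26% |
| 150:150 | 0.323 | 33% |
| 75:75 | 0.458 | 46% |

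The arithmetic is right for the counts used. It treats all 240 per arm as having an MMAS-4 score at 1 year.

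**2. Applying the plan's own dropout.** Section 13.2 allows 20% dropout, leaving about 190 per arm. Then 2.802 × √(2/190) = 0.287 SD, even if every survivor takes a relevant drug.

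**3. Allowing for non-users.** The documents give no figure for drug use among randomised survivors, so a range is assumed and applied equally to both arms.

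| Assumed use | n per arm (of 190) | Detectable difference | Power at 0.26 SD |
|---|---|---|---|
| 30% | 57 | 0.53 SD | 28% |
| 40% | 76 | 0.45 SD | 36% |
| 50% | 95 | 0.41 SD | 43% |

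These counts are for any relevant drug. If half of the 76 took a given class (a further assumption), the per-class count would be 38 per arm and the detectable difference 2.802 × √(2/38) = 0.64 SD.

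**4. Illustrating the selection.** Let b be the share on a relevant drug at baseline and s the share of the remainder who start one within the year, and assume no one stops.
- Scored survivors per arm = 190 × [b + (1 − b)s].
- Starters' share of those scored = (1 − b)s / [b + (1 − b)s].
- With no true effect on anyone's adherence, the spurious arm difference = (difference in starters' shares) × (starters' deficit in SD).

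All inputs except the 190 are assumptions.

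| b | s, control vs intervention | Starters' share | Deficit | Spurious difference | Rejection at nominal 5% |
|---|---|---|---|---|---|
| 50% | 10% vs 20% | 0.05/0.55 = 9% vs 0.10/0.60 = 17% | 0.5 SD | 0.04 SD | about 6% |
| 40% | 10% vs 30% | 0.06/0.46 = 13% vs 0.18/0.58 = 31% | 0.5 SD | 0.09 SD | about 9% |
| 40% | 10% vs 30% | 13% vs 31% | 1.0 SD | 0.18 SD | about 22% |
| 30% | 15% vs 40% | 0.105/0.405 = 26% vs 0.28/0.58 = 48% | 1.0 SD | 0.22 SD | about 28% |

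A milder set, with 40% vs 50% or 60% using a drug at 1 year and the extra users 0.25 to 0.5 SD apart from the rest, gives 0.05 to 0.17 SD and rejection of 6% to 20%. If the two arms' users are the same kind of people in the same proportions, the bias is 0 and rejection is 5%. If starters adhere better than established users, every sign reverses.

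**The case against.** The strongest reply is that the restriction to users at 1 year is nowhere stated. Table 4 describes the baseline questionnaire, follow-up uses an abridged version that is not shown, and a recent stopper might still be asked about the drug. This stands as a limit on certainty. The restriction is an inference from class-specific administration and from the baseline wording. It is firm for survivors who never took a drug and weaker for recent stoppers.

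Second, differential drug starting is an aim, not a finding. Controls and their providers also receive abnormal results with advice to seek follow-up, and section 7.4 concedes that participation alone may help them. Many survivors qualify through findings for which the protocol puts lifestyle change first. The expected 80% newly diagnosed overlaps with 40% undertreated, so it should not be read as 80% drug-naive. This also stands: the size, and even the existence, of the imbalance is unknown.

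Third, the plan has partial mitigations. Table 4 promises a secondary analysis by medication burden, section 13.3 compares drug prescriptions and treatment intensity by arm, and results may be stratified by initial underdiagnosis or undertreatment. These would help a reader notice an imbalance but would not remove it. The stratification is optional, and section 3.3.1 counts survivors managed by lifestyle alone as undertreated, so diagnosis status is not baseline drug use.

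Fourth, the intent-to-treat statement is limited to available end points, and adherence is one component of a secondary endpoint. The stakes are indeed modest. The qualifier does not rescue the label, because having an end point here is itself a post-randomisation event that the trial targets. Section 13.3's appeal to upfront randomisation concerns reporting bias and does not protect a subset formed afterwards.

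**Conclusion.** The point holds as a matter of structure. As far as the documents show, the 1-year adherence comparison will be made among survivors with a score at follow-up. Membership of that group can be affected by the intervention, so the comparison is not intent-to-treat.

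A reader might go further and infer that the result will be biased against the intervention by a known amount. The documents do not support that. Baseline drug use, start rates and the starters' deficit are all assumed. The 0.04 to 0.22 SD range, with 6% to 28% false rejection, only shows that the bias could run from negligible to close to the 0.26 SD the plan hopes to detect, and in either direction. Nor do the documents say that stoppers are excluded; they give no rule at all.

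One part needs no assumption about drug use. Table 10's 26% of 1 SD for MMAS-4 at 240:240 requires a score from every randomised survivor. At the plan's own 190 per arm it is 0.29 SD, and it grows once non-users are removed. The primary Aim 2 analysis is unaffected. This is a worthwhile, inexpensive correction to a secondary endpoint.

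**What to change.** In section 13.3:

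- Make the main between-arm adherence comparison in survivors who reported any relevant CV medication on the baseline questionnaire. Use one pre-stated summary of the class scores, such as the worst or the mean across classes taken at baseline, and adjust for the baseline score.
- Settle the direction of the scale first. Section 13.3 equates lower mean MMAS-4 scores with lower adherence, whereas Table 4 scores 0 as high adherence.
- State a rule that keeps survivors who stop in the comparison, for example counting them as lowest adherence in a rank-based analysis, with a sensitivity analysis that excludes them. Report stopping by arm. Without such a rule the baseline-user comparison would again be selected after randomisation.
- Present per-class results, and 1-year scores in all users including new starters, as descriptive and not as intent-to-treat, beside drug starts by arm.
- Restate the MMAS-4 detectable difference for the expected number of baseline users after 20% dropout. With 30% to 50% use (assumed), that is about 57 to 95 per arm, or 0.53 to 0.41 SD, and larger for any single class.

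The cost is analysis-plan wording. Baseline MMAS-4 is already collected, so no new data are needed. The downsides are a smaller comparison set, a less favourable detectable difference, and a question confined to survivors already on treatment at entry.

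### Aim 3 predicts an order across attitude typologies and compares a graded treatment-intensity scale, but names only an unordered chi-square test for each; an ordered test should be prespecified, with its limits stated

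*Combined protocol and SAP*

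**What the plan says.** **Attitudes** (13.3, Baseline survivor-specific factors). Using all Aim 1 participants, the plan asks whether the three typologies "are associated with differential rates of underdiagnosis and undertreatment [chi-square test"]. The next sentence sets an order in advance: "we hypothesize that the proportion undertreated will be greatest among" self-controlling survivors, with worried survivors marked as the "least undertreated) survivors", so collaborative survivors lie between. No trend test, score or contrast is named. A later sentence adds: "We also will use a combined logistic regression model to determine if knowledge, medication adherence, and health-related behavioral attitudes remain associated". It does not say how the typologies are coded.

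**Treatment intensity** (13.3, Post-intervention analysis; 8.8). The records analysis consists of "comparing [chi-square test] whether documentation rates differ across study arms of" CV screening, CV interventions, and treatment intensity with a pointer to Table 7. That table grades drug doses low, medium or high. Section 8.8 asks whether, among those undertreated at the first visit, "there is subsequent treatment intensification", with examples such as "from lower to higher drug doses; from single to multiple drugs". It also asks whether intensity differs between arms.

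The same section already names the Wilcoxon rank-sum test as an option for self-efficacy and MMAS-4 scores.

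**The concern.** A Pearson chi-square on three categories gives the same value however the categories are permuted. For attitudes, the plan states a ranking and then names a test that takes no account of it. For intensity, if the outcome is the Table 7 grade, a shift from low to high counts the same as any other rearrangement of the cells. What is at stake is some power in two secondary analyses, and a written link between the attitude hypothesis and a test that addresses it.

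**Working it through.** **The plan's own figures.** Table 10 is the only power statement for Aim 3. Its standard-deviation row follows from (1.960 + 0.842) × √(1/n₁ + 1/n₂):
- 320:480 gives 20.2%
- 240:240 gives 25.6%
- 150:150 gives 32.4%
- 75:75 gives 45.8%

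The table has 20, 26, 33 and 46%. A noncentral-t calculation gives 20.2, 25.6, 32.5 and 46.1%. The 25% and 60% rows also reproduce to the whole percent with a two-group chi-square. All of these are two-group comparisons, so the plan states no power for a three-category attitude test or for graded intensity.

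**General cost of ignoring a true, evenly spaced order** (α = 0.05, two-sided assumed). A 1-df test reaches 80% power at noncentrality 7.85. At that value a 2-df chi-square has 70.9% power and a 3-df chi-square 64.5%. To reach 80% they need noncentralities of 9.63 and 10.90, that is 23% and 39% more subjects.

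**Attitudes.** Inputs from the plan:
- N = 800.
- Undertreated = 0.60 × 0.40 = 24% (section 3.1.1).
- Typology frequencies from Table 10: 25% (self-controlling or worried) and 60% (collaborating). Taken as 25/60/25 these sum to 110, so I rescaled to weights w = 0.227/0.545/0.227.

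The typology-specific rates p below are assumptions, listed as worried/collaborative/self-controlling. With p̄ = Σwp and scores x = 0, 1, 2:
- Pearson (2 df): λ = N Σw(p − p̄)² / [p̄(1 − p̄)]
- Trend (1 df): λ = N [Σw(x − x̄)(p − p̄)]² / [p̄(1 − p̄) Σw(x − x̄)²]

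For 18/24/30%: p̄ = 0.24, Σw(p − p̄)² = 2 × 0.2273 × 0.06² = 0.001636, and λ = 800 × 0.001636 / 0.1824 = 7.18 for both tests.

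| Assumed rates | Pearson λ, power | Trend λ, power |
|---|---|---|
| 18/24/30% | 7.18, 67% | 7.18, 76% |
| 22/24/34% | 8.49, 74% | 6.84, 74% |
| 23/24/36% | 10.97, 85% | 7.89, 80% |
| 12/23/24% | 10.98, 85% | 7.97, 81% |
| 21/21/33% | 11.18, 86% | 7.23, 77% |

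Simulation with 40,000 runs agrees within about 2 points, except that 12/23/24% gives 89% against 82%.

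Direction: with the order reversed (32/24/16%) Pearson still rejects about 91% of the time. The two-sided trend test rejects about 95% of the time, with the opposite sign.

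**Intensity.** The plan gives 240 per arm and 20% dropout, so about 190 per arm. The control splits and odds ratios are assumptions. Under proportional odds, a control split of 50/30/20% has cumulative odds 1 and 4. Dividing by 1.75 gives 0.571 and 2.286, hence an intervention split of 36.4/33.2/30.4%. Simulated power at 190 per arm, 40,000 runs:

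| Control split | OR | Pearson (2 df) | Wilcoxon |
|---|---|---|---|
| 50/30/20% | 1.5 | 46% | 56% |
| 50/30/20% | 1.65 | 65% | 75% |
| 50/30/20% | 1.75 | 75% | 83% |
| equal thirds | 1.5 | 47% | 57% |
| equal thirds | 1.75 | 75–76% | 84% |

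The gain is about 8 to 10 points. It is about 4 points at OR 2.0, where both tests exceed 90%. At 150 and 75 per arm (the range section 13.2 gives for stratified analyses), with 50/30/20% and OR 1.75, the figures are 65% against 74% and 36% against 45%.

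If the outcome is intensified yes or no, the table is 2×2. The chi-square then has 1 df and nothing is lost.

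**The case against.** **The intensity outcome may be binary.** Section 13.3 speaks of documentation rates, and section 8.8 can be read as asking whether intensification occurred at all. On that reading the chi-square is suitable, as it is for the screening and intervention items in the same list. This stands as a limit: the point applies only if the grade is analysed. The pointer to Table 7 makes that reading natural, but the plan does not settle it. Nor does it hypothesise any order for intensity, so a complaint that a stated order goes untested applies to attitudes only.

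**A fourth level is not in the plan.** Adding a none category enlarges the gain (about 55–56% against 72% at OR 1.6 with an assumed 40/25/20/15% split). Table 7 has no such level, and the visible text gives no rule for combining drugs into one grade per person. I therefore rest the size on three levels.

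**The trend test is not always better.** A reader might infer that a chi-square always loses power against an ordered alternative. The table above shows otherwise, even for monotone patterns. The plan does not say that the steps are even, and Aim 3 Hypothesis 1 singles out the self-controlling group, which is the kind of pattern where equal scores do worse.

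**A trend test does not prove the ranking.** This is also correct. A two-sided trend test is as significant under the reverse order, and at 21/21/33% it rejects 77% of the time although worried and collaborative survivors do not differ. The sign and the group proportions must be read with either test. The logistic model could supply directional estimates, but its coding is not given.

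**Conclusion.** The point holds in a limited form. The attitude hypothesis is ordered and no ordered test or contrast is named for it. Treatment intensity is compared by a test that ignores the Table 7 grading, if that grade is the outcome. For three-level intensity at 190 per arm, the expected gain from a rank test is about 8 to 10 points for odds ratios of 1.5 to 1.75. For attitudes the effect runs from a gain of about 10 points with even steps to a loss of 5 points or more when one gap dominates.

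The documents do not support a claim that the planned tests are invalid, or that they lose power in general. Nor should the attitude calculation be centred on 60%: that is the expected share with any abnormal finding, whereas the order is stated for the undertreated, about 24%. The 60% base applies only if underdiagnosis is pooled in.

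All typology-specific rates, intensity splits, odds ratios and the two-sided level are assumptions. Both analyses lie outside the Aim 2 primary outcome, so this is an optional improvement.

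**What to change.** 1. **Intensity.** State whether the outcome is the ordered Table 7 grade or intensification yes/no, and, if graded, how one grade per participant is formed. Compare a graded outcome between arms with a Wilcoxon rank-sum test or a proportional-odds model. Keep the chi-square for yes/no items: screening, interventions, and intensification if it is binary.
2. **Attitudes.** Prespecify a 1-df ordered contrast or trend test (worried < collaborative < self-controlling), with its scores fixed before analysis. Report it with its sign and the three group proportions. Keep the 2-df chi-square as the global check, which protects against uneven spacing. State the coding of the typologies in the logistic model.

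The cost is wording in section 13.3, with no new data and no change in sample size. The drawback is the possible loss of power for the attitude contrast under uneven steps, so the text should say which test is the main one for the hypothesis and should not claim that it establishes the full order.
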